### 5.5.4 Secondary analysis

### 5.5.4.1 Nasal scraping procedures

Descriptive statistics of RNA results will be summarized by smoker and never smoker groups using total number of observations (n), mean, median, standard deviation, quartiles (Q1 and Q3) and minimum and maximum values.

Nasal scraping procedures will be presented for FAS dataset as described in Table A 9.

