**Clinical Study Protocol** 

Confidential

P1-CMS-01-US

Final 2.0 Amendment 1.0, 22-May-2017

Page 41 of 106

Related to PMI\_RD\_WKI\_000759

test performed immediately after smoking (5-10 minutes post T0). T0 will be defined as the start of cigarette smoking for smokers (time point of first product use during study day). T0 should be the same for all smokers within an acceptable time window of 1 hour. Never smokers will also have the STT test performed in the morning at 8 am  $\pm$  30 minutes (designated T0 $\pm$  30 minutes). All study participants (smokers and never smokers) will then have the STT test performed until 4h30 min), 8h (may be performed until 8h30 min), and 12h (may be performed until 12h30 min) post T0, ensuring at least approximately 4 hours between the beginning of each STT test. The participant will be asked to confirm he can no longer feel the sweet taste. Study participants will drink a glass of water (approximately 240 mL) before STT tests are performed.

Samples for plasma nicotine assessment will be collected at approximately the same time points that STT test is performed at  $T_0$ , 4h (may be performed until 4h30 min), 8h (may be performed until 8h30 min), and 12h (may be performed until 12h30 min) post  $T_0$ .

Nasal scraping of the inferior turbinate of both nostrils will be performed on all 14 study participants at the end of Visit 3, after all other clinic assessments, except the brief physical examination which will be done after the nasal scraping:

- For 4 study participants, the nasal scraping (left nostril with method 1, right with method 2) will be performed and samples collected for subsequent histological assessment.
- For the 10 remaining study participants, 5 will undergo nasal scraping using method 1, and 5 using method 2. For all 10 study participants, cells from one nostril will be added into one buffer, cells from the other nostril into a second buffer. Samples will be collected for subsequent RNA quantity and quality analysis.

Full procedure is described in the "Method establishment to obtain human nasal epithelial sample using the Rhino-probe".

Upon conclusion of all clinic assessments, at the time of discharge on Visit 3, the Principal Investigator or designee will perform a brief physical examination on the study participant.

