# 7.2.8.8 Nasal scraping, sical assessment and biological specimen collections for further analysis

See Appendix A - Schedule of Events for the timepoints of assessment.

Nasal scraping of the inferior turbinate of both nostrils will be performed on all 14 study participants as described in the separate document "Method establishment to obtain human nasal epithelial sample using the Rhino-probe".

For 4 study participants, nasal scraping (left nostril with method 1, right with method 2) will be performed and cell samples will be collected, processed, appropriately labeled and shipped by the study site as per the "Method establishment to obtain human nasal epithelial sample using the Rhino-probe" to the appropriate laboratory for further histological assessment.

For the 10 remaining study participants, 5 will undergo nasal scraping using method 1, and 5 using method 2. For all 10 study participants, cell sample from one nostril will be added into one buffer and cell sample from the other nostril into a second buffer. Samples will be collected, processed, appropriately labeled and shipped by the study site as per the "Method establishment to obtain human nasal epithelial sample using the Rhino-probe" to the appropriate laboratory for subsequent RNA quantity and quality analysis.

RNA quantity and quality will be assessed as per the Sponsor internal laboratory SOPs. RNA from the nasal sample will be extracted. Then a quantification step will occur using a Nanodrop 1000 instrument (TermoFisher scientific).

The quality will be assessed by using a Bioanlayzer 2100 (Agilent Technologies): the Bioanalyzer delivers a mark from 1 to 10 (10 is the best) to give an idea of the quality and integrity of the RNA (RIN value stands for RNA integrity Number).

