# **12** PLANNED STATISTICAL METHODS

# **12.1** General Considerations

Full details of the statistical analysis will be given in a Statistical Analysis Plan (SAP). Any changes to the planned statistical methods will be documented in the Clinical Study Report. The statistical evaluation will be performed using SAS®, version 9.2 or later.

STT for each time point will be summarized by smoker and never smoker group using the descriptive statistics: mean, minimum, maximum, median, quartiles, standard deviation (SD) and 95% confidence interval (CI).

The plasma nicotine levels for each time point will be summarized by smoker and never smoker group using the descriptive statistics mean, minimum, maximum, median, quartiles, standard deviation (SD) and 95% confidence interval (CI).. The relationship between plasma nicotine levels and STT at each time point will be evaluated by spearman correlation as well as graphical presentation of these endpoints by time point and smoker and never smoker group.

An overall summary of AEs will be presented by smoker and never smoker group showing the number of events and percent of study participants who experienced AEs, SAEs, severe AEs and AEs leading to study discontinuation.

RNA concentration will be summarized by method using descriptive statistics: mean, minimum, maximum, median, quartiles, standard deviation (SD) and 95% confidence interval (CI)..

RNA RIN will be summarized by method using descriptive statistics: mean, minimum, maximum, median, quartiles, standard deviation (SD) and 95% confidence interval (CI).

A summary of AEs by System Organ Class (SOC) and Preferred Term (PT) by smoker and never smoker group will be presented.

Vital signs will be summarized by smoker and never smoker group using descriptive statistics: mean, minimum, maximum, median, quartiles, standard deviation (SD) and 95% confidence interval (CI)..

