#### 5.5 Statistical analysis

All quantitative variables will be summarized through descriptive statistics namely mean, median, standard deviation, quartiles (Q1 and Q3) and minimum and maximum values. Qualitative variables will be summarized through number (n) and frequency distribution (%).

All descriptive analyses will be performed by smoker and never smoker group.

Statistical tests will be two-tailed considering a significance level of 5%.

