### Table A 9 – Nasal scraping at visit 3 – FAS population

	Total (n=xx)
Method, n (%) Left nostril (method 1) Right nostril (method 2) Total	
Only method 1 (5 subjects) RNA N Mean Median Standard Deviation Q1 Q3 Minimum Maximum	
Only method 2 (5 subjects) RNA N Mean Median Standard Deviation Q1 Q3 Minimum Maximum	
Method 1 or 2 (10 subjects) RNA N Mean Median Standard Deviation Q1 Q3 Minimum Maximum	
Method 1 and 2 (4 subjects) RNA N Mean Median Standard Deviation Q1 Q3 Minimum Maximum	

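### RNA results: SAP 5.5.4.1 groups by smoking status where Protocol 12.1 and SAP Table A 9 group by scraping method, and Table A 9 merges concentration with RIN, omits the 95% CI and plans RNA statistics for four histology participants

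*SAP*

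**What the plan says.** **Protocol.** Section 12.1 treats quantity and quality as separate variables: "RNA concentration will be summarized by method using descriptive statistics", and "RNA RIN will be summarized by method using descriptive statistics". Both summaries are to include a 95% CI, and the synopsis agrees. Section 7.2.8.8 obtains them from different instruments: a Nanodrop for quantity, and a Bioanalyzer giving RIN on a scale from 1 to 10.

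Sections 4.1 and 7.2.8.8 split the 14 participants. Four have one nostril scraped with each method, with "samples collected for subsequent histological assessment". The other ten (five per method) supply the RNA samples, and for each of them "cell sample from one nostril will be added into one buffer and cell sample from the other nostril into a second buffer".

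**SAP.** Section 5.5 sets a general rule: "All descriptive analyses will be performed by smoker and never smoker group". Section 5.5.4.1 applies it to the scraping data: "Descriptive statistics of RNA results will be summarized by smoker and never smoker groups". It lists n, mean, median, SD, quartiles, minimum and maximum, with no CI, and refers the reader to Table A 9.

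Table A 9 has one Total column and no smoking-group columns. Its RNA blocks are method 1 only ("Only method 1 (5 subjects) RNA N Mean Median"), method 2 only (5 subjects), the two pooled (10 subjects), and "Method 1 and 2 (4 subjects) RNA N Mean Median". The variable is called RNA throughout, without a unit, and SAP Appendix 1 does not define it.

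**The concern.** Protocol 2.1 and 4.2 give the purpose of using two methods: to find the one that gives the most RNA and the best RNA, for later transcriptomic work. A summary by smoking group does not address that, because each group can contain participants scraped with either method. A single RNA row cannot report quantity and integrity as two results.

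The programmer would have to decide three things the plan should settle: whether the text or the table governs, which measure RNA stands for, and whether two samples from one person count once or twice. None of the 15 planned listings shows RNA values, so a reader of the outputs could not see which choices were made.

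**Working it through.** The plan gives no numerical claim to reproduce on this point. The check is a comparison of the texts, then a count of the data, then the precision available.

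**1. Texts side by side**

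| Item | Protocol 12.1 | SAP 5.5.4.1 | SAP Table A 9 |
|---|---|---|---|
| Grouping | method | smoking group | method, one Total column |
| Variables | concentration and RIN | RNA results | RNA, no unit |
| 95% CI | yes, for both | no | no |
| Participants with RNA data | 10 (from sections 4.1 and 7.2.8.8) | not stated | 10, plus a block for 4 more |

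Version lag does not explain the mismatch. The SAP was written to protocol version 1.0, and the protocol's revision history to version 2.0 lists only the age-range change.

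**2. Counts**

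- Participants: 4 + 5 + 5 = 14, of whom 5 + 5 = 10 give RNA samples.
- RNA samples: 10 × 2 nostrils = 20. Values: 20 × 2 measures = 40.
- Per method: 5 participants and 5 × 2 = 10 samples, or 5 samples in each method-by-buffer cell.
- The four-subject RNA block has no planned RNA data (N = 0).

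**3. What a smoking-group summary would contain.** The documents do not say how smokers are spread over the histology and RNA subsets. Between 0 and 4 of the 7 smokers could be in the histology subset, which leaves 3 to 7 smokers, and correspondingly 7 to 3 never smokers, among the ten. The split of methods within each smoking group is also unstated.

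**4. Precision by method, with the participant as the unit** (t-based 95% CI half-widths, in units of the SD of the value analysed)

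- One method mean, n = 5: t(4; 0.975)/√5 = 2.776/2.236 = 1.24 SD.
- Method difference, 5 vs 5: t(8; 0.975) × √(2/5) = 2.306 × 0.632 = 1.46 SD.

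**5. Effect of counting both nostrils as independent.** With n = 10 samples, the half-width for one method mean would be t(9; 0.975)/√10 = 0.72 SD, where SD is now that of a single sample. Let ρ be the within-person correlation, and ignore any buffer difference. A participant mean of two samples then has SD × √((1 + ρ)/2), so the half-width based on 5 participants is 1.24 × √((1 + ρ)/2). That is 1.24 × 0.707 = 0.88 SD at ρ = 0 and 1.24 SD at ρ = 1. The documents do not give ρ, so this is a range. Over all of it, the ten-sample interval is the narrower one.

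**The case against.** The best defence is that SAP 5.5.4.1 itself sends the reader to Table A 9, which is by method, and SAP section 1 singles out the table shells as reviewed and approved by the sponsor's representative. On that view the right comparison would be produced, and the offending sentence is a slip carried over from the general rule in 5.5. This lowers the practical risk on grouping, but it does not remove the contradiction, and following the table still leaves the merged variable, the missing CI and the four-subject block.

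Some lesser objections have force:

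- **Missing CI.** It is not special to RNA, since vital signs lose theirs in the same way. It can be recomputed from N, mean and SD, and would be wide.
- **Shell rows.** The shells as read from PDF lack expected rows elsewhere, so one absent row is weak evidence. Here, however, all four RNA blocks agree, and the text also omits the CI.
- **Four-subject block.** It would print as empty and bias nothing. The full scraping procedure is in a separate document not available here, though the protocol itself gives those samples only a histology use.
- **Unit of analysis.** The block labels count subjects, which hints at the participant. Protocol 12.1 is silent on this and on buffers, so this is a gap and not a contradiction.
- **Listing.** No text requires an RNA listing, and plasma nicotine has none either.
- **SAP section 6.** It deals only with analysis populations, so its silence on this change adds little.

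**Conclusion.** The point holds as stated. SAP 5.5.4.1 conflicts with Protocol 12.1 and with Table A 9 on grouping. Table A 9 puts 40 planned values of two different measures under one undefined name, both SAP places drop the protocol's 95% CI, and one of the four RNA blocks has no data under the protocol's allocation. The four-subject finding assumes that the separate scraping procedure does not add an RNA use for those samples.

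The consequence is limited. The objective is secondary and descriptive, no hypothesis is tested, and the primary analysis is untouched. With 5 participants per method, intervals of ±1.24 SD for a mean and ±1.46 SD for a difference keep the results descriptive whatever layout is used. It should be corrected before the analysis is programmed.

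**What to change.** In the SAP:

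1. Reword 5.5.4.1 to summarise by scraping method, and exempt it from the smoking-group rule in 5.5.
2. Split Table A 9 into RNA concentration (with unit) and RIN, each by method for the ten RNA participants, with a 95% CI.
3. State the unit of analysis: either show results by buffer (5 per method-by-buffer cell) or use participant means, so that two nostrils of one person are not counted as independent.
4. Delete the four-subject RNA block, or reconcile it with the histology allocation.
5. Add a listing by subject, method, nostril and buffer.

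Two additions are optional. One is a descriptive method difference (5 vs 5) with its 95% CI. The other, if the separate scraping procedure does not already provide for it, is to balance the 5/5 method split across smoking groups.

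The cost of items 1 to 5 is some SAP text, one revised table shell and one new listing. They need no extra samples or participants and no change to nostril assignment.

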### 5.5.4.2 Safety analysis

Vital signs (systolic blood pressure, diastolic blood pressure, pulse rate and respiratory rate) will be summarized by total number of observations (n), mean, median, standard deviation, quartiles (Q1 and Q3) and minimum and maximum values.

An overall summary of AEs will be presented by smoker and never smoker groups showing the number of events and percent of study participants who experienced AEs, SAEs, severe AEs and AEs leading to study discontinuation.

A summary of AEs by System Organ Class (SOC) and Preferred Term (PT) according to Medical Dictionary for Regulatory Activities (MedDRA) by smoker and never smoker groups will be presented.

Each parameter of hematology, clinical chemistry and urine will be summarized over time by smoker and never smoker group thought total number of observations (n), mean, median, standard deviation, quartiles (Q1 and Q3) and minimum and maximum values. Number (n) and frequency distribution (%) of normal and abnormal values will also be present by each parameter.

All safety analyses will be performed for the safety dataset only.

Vital signs measures will be presented for safety dataset in Table A 10 and listed in Listing 12

Incidence and frequency distribution of AEs, SAEs, AEs with reasonable possibility of relationship with study drug will be presented in **Table A 11** and **Table A 12**. All adverse events and serious adverse events will also be listed by subject in **Listing 13** and **Listing 14**.

Regarding laboratory parameters, results of hematology, chemistry and urinalysis will be presented for safety dataset in **Table A 13**, **Table A 14** and **Table A 15** and listed by subject in **Listing 15**. Results on serology at visit 1 will be presented in **Table A 16**.

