# 4.4 Study Duration

The planned maximum study duration for a single study participant from Screening through completion of study will be 33 days.

The estimated maximum study duration for the whole Study from screening through completion will be 35 days.

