#### **Confidentiality Statement**

Data and information contained in this document are considered to constitute trade secrets and confidential commercial information, and the legal protections provided to such trade secrets and confidential information are hereby claimed under the provisions of applicable law. No part of this document may be publicly disclosed without the written consent of Philip Morris Products S.A.

Final 2.0 Amendment 1.0, 22-May-2017

Related to PMI RD WKI 000759

i. A positive urine cotinine test ( $\geq 200$ ng/mL).

- ii. Smoked at least 20 cigarettes per day for at least the past 5 years.
- iii. eCO levels >10 parts per million (ppm).
- iv. No plans to quit smoking in the next 3 months.
- b. Never smoker (meets all of the following criteria at Visit 1 and at Visit 2):
  - i. Subject who has smoked less than 100 cigarettes throughout their lifetime and no cigarettes in the past 3 years.
  - ii. A negative urine cotinine test (<200 ng/mL).
  - iii. eCO levels  $\leq$  5 ppm.
- 6. Completed the Screening process within 30 days prior to Visit 2.
- 7. Availability for the entire study period and willingness to comply with study procedures, including smoking interruptions, as evidenced by a signed ICF and at Visit 2.

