# 8.2.2 Period of Collection

Starting from the time when consent was obtained, the PI or designee will record all adverse events observed, queried, or spontaneously reported by the study participants. An adverse event query will be performed as scheduled as per Principal Investigator or designee's direction at the screening visit and throughout the confinement period and prior to being released from

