# **9.2** Confinement Period (Day 1 to Day 2)

During Visit 2, selected inclusion and exclusion criteria will be reassessed to ensure study participants are still eligible for enrollment (Appendix B – Inclusion and Exclusion Criteria Assessment). All study participants will have baseline assessments performed (Appendix A), including STT test.

Study participants will be confined in the clinic from the beginning of Visit 2 until discharge at Visit 3. During this confinement period study participants will abstain from drinking any alcohol and any drinks containing caffeine. Standard meals will be served. Drug restrictions applicable to study participant exclusion will also be maintained until the end of the study.

No cigarettes are to be smoked from midnight ( $\pm 1$  hour) between Visit 2 and Visit 3 until 8 am on the day of Visit 3. On the day of Visit 3, at least 8 hours after last cigarette, CC smokers, who want to smoke, will have a cigarette at 8 am $\pm 30$  minutes and then have the STT test performed immediately after smoking (5-10 minutes post T0). T0 will be defined as the start of cigarette smoking for smokers. T0 should be the same for all smokers within an acceptable time window of 1 hour. Never smokers will also have the STT test performed in the morning at 8 am  $\pm 30$  minutes (designated T0 $\pm 30$  minutes). All study participants (smokers and never smokers) will then have the STT test performed at 4h (may be performed until 4h30 min), 8h (may be performed until 8h30 min), and 12h (may be performed until 12h30 min) post T0, ensuring at least approximately 4 hours between the beginning of each STT test. The

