# **9.3** Safety Follow-Up Period

From the Discharge on Visit 3, the study participant will enter a 1-day Safety Follow-Up Period during which spontaneously reported new AEs/serious AE (SAE)s will be recorded, and the active follow-up of ongoing AEs/SAEs will be done by the site with a phone call to the study participant.

Any non-serious AE that is ongoing during the Safety Follow-Up Period will be actively followed-up by the Principal Investigator or designee during that period until it has been resolved, stabilized (i.e., no worsening of the condition), or an acceptable explanation has been found (e.g., a chronic condition).

At the end of the Safety Follow-Up Period, all ongoing non-serious AEs will be documented as "ongoing" and no follow-up information will be sought for on them anymore by the Principal Investigator or designee. At that point, the Investigator will assess whether the subject should be referred to his/her General Practicioner to have their ongoing AEs addressed accordingly.

All SAEs will be followed up by the Investigator or designee, despite their continuation after the end of the Safety Follow-Up Period, until their resolution, stabilization (i.e., no worsening of the condition), or an acceptable explanation has been found (e.g., a chronic condition).

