# **11.2** Data Handling

All study data will be managed by the Data Management Team at the CRO. The Data Management Team at the CRO will prepare a Data Management Plan (DMP). This document will describe, in details, the Data Management-related procedures and processes. The overall procedures for quality assurance of clinical study data are described in the SOPs of the CRO Data Management Team and/or Data Management Plan (DMP).

Data of all study participants enrolled, including screening failures and AE during the study (from the time of Informed Consent to the end of the safety follow-up period) will be captured in the source documents. All enrolled subjects will be entered in the study database (eCRF).

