#### Table A 11 – Overall summary of adverse events – Safety population

	Smoker (n=xx)		Never sm (n=xx)	noker
	n (%)	nAEs	n (%)	nAEs
Any adverse event, n (%) Any serious adverse event, n (%)				

Any severe adverse event, n (%) Any adverse event leading to study discontinuation, n (%)

n (%) = Number (percent) of subjects. nAE = Number of adverse events.

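### Tables A 11 and A 12 pool all AEs from consent to the end of follow-up, a window of 4 to 33 days per man, with no split by onset and no row for procedure-related events

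*SAP*

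**What the plan says.** Protocol 8.2.2 sets the start of collection: "Starting from the time when consent was obtained, the PI or designee will record all adverse events observed, queried, or spontaneously reported". Protocol 11.2 gives the span of capture as "from the time of Informed Consent to the end of the safety follow-up period".

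The length of that span varies by man. Inclusion criterion 6 (Protocol 5.1.1) reads "Completed the Screening process within 30 days prior to Visit 2", and Appendix A places Visit 1 anywhere from D-30 to D-1. Confinement is Day 1 and Day 2 (Protocol 9.2). After discharge, "the study participant will enter a 1-day Safety Follow-Up Period" (Protocol 9.3), which is D3 in Appendix A. Protocol 4.4 adds: "The planned maximum study duration for a single study participant from Screening through completion of study will be 33 days".

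Enrolment is marked at Visit 2 in Appendix A, and the safety population is everyone enrolled (SAP 5.3.3).

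On the summary, SAP 5.5.4.2 says: "An overall summary of AEs will be presented by smoker and never smoker groups showing the number of events and percent of study participants". The shell of Table A 11 opens with a row beginning "Any adverse event, n", followed by rows for serious AEs, severe AEs and AEs leading to discontinuation. Table A 12 has rows by SOC and PT. Both have columns only for group, each with number of subjects and number of events. The same SAP section also promises, in these two tables, AEs possibly related to a study drug. Neither shell has a row for related AEs, and Protocol 8.2.4 says that there is no investigational product and that causality is judged against study procedures.

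**The concern.** A percentage of men with at least one AE is easy to read when all men are observed for about the same time. Here the observation time is set largely by how soon each man could be booked for Visit 2. Two men with the same underlying risk have different chances of being counted, and the tables carry no person-time or period column to show it.

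The pooled count also mixes different situations: the Visit 1 clinic day, an unsupervised interval at home, the confinement with its cigarette, repeated STT tests and blood draws, and the hours after nasal scraping. Protocol 2.3.2 gives risk from study procedures as the reason for the follow-up day, but no summary table lets a reader see events around those procedures. The missing related-AE row removes the other way of doing so.

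There is also a selection feature. A man with a disqualifying event between visits becomes a screen failure (Protocol 5.4) and leaves the safety population, so the pre-Visit-2 counts describe only men who remained eligible.

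At stake is how clearly the descriptive safety summary can be read.

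**Working it through.** **Inputs.** Screening interval w = 1 to 30 days (Appendix A; inclusion criterion 6). Confinement = 2 days (Protocol 9.2). Follow-up = 1 day (Protocol 9.3). Group size 7 and 7 (SAP 5.1).

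**Reproducing the plan's figure.** 30 + 2 + 1 = 33 days, which matches the stated maximum in Protocol 4.4.

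**Window per completing man.** Length = w + 3. The minimum is 1 + 3 = 4 days and the maximum 30 + 3 = 33 days, a ratio of 33/4, or about 8.

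**Share of the window before Visit 2** = w/(w + 3):

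| Wait w (days) | Window (days) | Share before Visit 2 |
|---|---|---|
| 1 | 4 | 25% |
| 3 | 6 | 50% |
| 7 | 10 | 70% |
| 14 | 17 | 82% |
| 30 | 33 | 91% |

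These are shares of calendar days, not of AEs. Visit 1 is itself a clinic day with a skin prick test, post-bronchodilator spirometry, STT and blood sampling. The fully at-home share at the maximum is therefore 29/33 = 88%.

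**Sensitivity of one man's chance of being counted.** The documents give no background AE rate. Assume a constant rate r per man-day, over a range chosen only for illustration. The chance of at least one background AE is then 1 - exp(-r × days):

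| Assumed r per day | 3 days (Visit 2 onward) | 4 days (w = 1) | 33 days (w = 30) |
|---|---|---|---|
| 0.005 | 1.5% | 2.0% | 15.2% |
| 0.01 | 3.0% | 3.9% | 28.1% |
| 0.02 | 5.8% | 7.7% | 48.3% |
| 0.05 | 13.9% | 18.1% | 80.8% |

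The last two columns compare the extreme waits for a single man and are not a forecast for groups. A constant rate probably overstates the pre-Visit-2 part, because eligibility is checked again at Visit 2 and men with disqualifying events drop out. The 3-day column shows what a split achieves: from Visit 2 onward, the chance no longer depends on w.

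**What the shells can show.** Tables A 11 and A 12 have group columns only: no onset cut-off, period column, person-time or related row. Listing 13 has start date and relationship to study procedures for each AE. Protocol 8.2.1 also records onset time, which Listing 13 does not display.

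**The case against.** The strongest reply is that this is a 14-man descriptive study with no hypotheses. One man is 100/7 = 14.3 percentage points, so no AE percentage here can support a group contrast, even with equal windows. Counting from consent agrees with the Protocol's collection rule and with the secondary objective, which is to monitor safety during the study. The investigator judges each event against study procedures, and Listing 13 can be read in full for 14 men. All of this stands, and it keeps the point small.

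Four stronger readings are tempting, and the documents do not support them:

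- **That pooling will create a difference between smokers and never smokers.** This would need waits that differ by group. Both groups share the same screening window, and nothing suggests that one waits longer. The 4-day and 33-day chances would become a group contrast only if every man in one group waited 1 day and every man in the other 30.
- **That the pre-Visit-2 counts will be full of colds.** Exclusion criterion 13 bars upper or lower respiratory disease in the 4 weeks before Visit 2 and is checked at both visits (Appendix B), so most such men would not be enrolled. Other minor events remain possible.
- **That the safety objective is about study procedures only.** It is not limited in that way. The procedure focus comes from the rationale for the follow-up day (Protocol 2.3.2) and the causality rule (Protocol 8.2.4).
- **That pre-Visit-2 events are mere background and can be set aside.** Visit 1 includes a skin prick test, bronchodilator spirometry, STT and blood draws. Reactions to these are procedure events and must stay visible as such.

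The reply does not remove one fact: the two summary tables carry counts that depend partly on booking, and they cannot show when an event began or whether it was related to a procedure.

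**Conclusion.** The point holds as a minor improvement to two table shells. For men who complete the study, the AE window runs from 4 to 33 days, with 25% to 91% of it before Visit 2, and the pre-Visit-2 events counted are only those of men later enrolled. The pooled n (%) therefore depends partly on the wait and does not isolate events around the confinement procedures.

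The size of the effect is unknown. It depends on the actual waits and the background AE rate, and the documents give neither; the percentages shown above rest on an assumed constant rate. If waits turn out short or similar, the distortion will be small. Data collection is not at fault, because start date and relationship are held for each event. A reader might infer that the planned tables hide a procedure signal, but Listing 13 lets each event be traced by hand.

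**What to change.** In Tables A 11 and A 12, keep the overall total and add columns by AE onset:

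- (a) Visit 1 consent to before Visit 2 admission
- (b) Visit 2 admission to before nasal scraping
- (c) nasal scraping to end of follow-up

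If onset time is missing, split by date at Visit 2 only.

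Add a row for AEs related to study procedures in every period, and replace the study-drug wording in SAP 5.5.4.2 to match Protocol 8.2.4. Reactions to Visit 1 procedures then appear in column (a) as procedure events. Add onset time to Listing 13 where it was recorded. State in 5.5.4.2 that groups are compared descriptively on the columns from Visit 2 onward, where each completing man has about the same 3-day window.

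The cost is a few sentences of SAP text and two re-laid shells, with no new data. The downside is slightly larger tables with small counts per cell.
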